**Figure 1.**

**Figure 1:** Diagram of patient management and timepoints where the [F] FMISO studies will be done in the course of treatment. FMISO PET #1 will be performed prior to treatment. FMISO PET #2 will be performed 1 month after all TACE procedures (in case multiple TACE procedures are performed) and prior to SBRT, and FMISO PET #3 will be performed 1 month following the end of liver stereotactic radiation therapy. 20 patients will be enrolled in this study.

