## **7. STATISTICAL CONSIDERATIONS**

### **7.1 Study Design/Endpoints**

This is a Phase II study of a PET imaging agent, [F]FMISO, in patients with HCC who will be receiving standard care with TACE, and with radiation. The imaging study will not impact the patient's treatment. The objective of this study is to evaluate the potential of [F]FMISO as a non-invasive indicator of tissue hypoxia in HCC patients to provide tumor imaging data.

The primary endpoint is changes in [F]FMISO parameters (HV and T:Bmax) between baseline and follow-up scans. The regional tissue: blood values will be determined and hypoxic volume of the primary tumor and metastases will be calculated. The number of pixels in the tumor volume with a T/B ratio  $\geq 1.2$ , indicating significant hypoxia, will be determined and converted to milliliter units to measure the HV. In each tumor region, we will also locate the pixel with the maximum T/B ratio and include this variable, T/Bmax, in our analysis. HV evaluates the volume of tumor that has crossed the threshold for hypoxia and T/Bmax depicts the magnitude of hypoxia.

The exploratory endpoints include overall survival (OS), disease free survival (DFS) and response to XRT by RECIST, mRECIST or EASL (because enhancement changes are known to better reflect treatment response than size changes) criteria.

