### **7.2 Sample Size/Accrual Rate**

This is a Phase II study in patients with Hepatocellular Carcinoma (HCC). We propose a sample size of 20 patients for this initial clinical trial because of patient recruitment based on low HCC incident from UAB tumor register data. If the results are promising but inconclusive, they will be used to define a larger multi-center trial. We expect to have a full enrollment in 2 years. From the previous study (Rajendran 2006), a significant hypoxia was identified in 58 patients (79%) in head and neck cancer. The mean

FMISO T/Bmax was 1.6 (range 1.0–3.5) and the mean HV was 40.2 mL (range 0–1092). We expect at least 60% hypoxia/uptake (e.g. TB ratio changes from baseline >1.2) will be identified in HCC patients in this study, thus with a size of 20 patients we will be able to have an accurate estimation of patients who will have undertaken of [F] FMISO with ~ 10% error, and produces a two-sided 95% confidence interval with a width equal to 0.448 for each FMISO PET scan. The size will be also able to evaluate pre-post changes of 1.5 effect size for T/Bmax based on the above published data using one group paired t-test with >80% power at 5% alpha level. Due to the nature of exploratory to generate hypothesis data for future study, the intra correlation between FMISO PET scans within the same subject will not considerate in the sample size consideration this time.

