### 7.3 Statistical analysis plan

The primary endpoint analysis of changes in [F]FMISO parameters (HV and T:Bmax) between baseline and 2 follow-up scans will be using paired t-test. Proportion of patients with uptake of [F] FMISO will be reported as N and % and exact 95% confidence interval using the method of Clopper-Pearson. Descriptive analysis such as mean, standard deviation at baseline and follow-up will be estimated with two-sided 95% confidence intervals for all [F]FMISO parameters from PET scans. Longitudinal analysis will be also applied to estimate the changes (slope) between baseline to the first treatment of TACE and sequential treatment of Stereotactic Radiotherapy (SBRT) with auto correlation covariance structure to control patients' intra-correlation. When repeat studies are done sequentially over the course of treatment, changes are expected to be substantial.

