The exploratory endpoints analysis include using cox regression analysis to correlate [F]FMISO parameters with overall survival and progression free survival; and using logistics regression analysis to associate [F]FMISO parameters with clinical response (yes, no). Baseline [F]FMISO, FU [F]FMISO, and changes of [F]FMISO between baseline and FU will be used individually in order to identify if early image of [F]FMISO at baseline, and treatment with TACE alone (FU1) and with radiation (FU2) can predict survival or response. Survival is defined from the time of initial PET scan to the last follow up. Patient's demographics and other prognosis factors will be adjusted in the model. The set of prognostic variables considered in the analysis include standard clinical measures (age, tumor-node-metastasis status), as well as the PET measurements [HV, and FMISO tissue to blood ratio (T/Bmax)]. Due to the high correlation between HV and T/Bmax, and the resulting issue of multicollinearity, these variables will each considered separately with the other prognostic variables. Hazard ratio and Odds ratio will be estimated along with 95% CI. Log-rank tests will be used to compare Kaplan-Meier survival curves associated with patients above and below the median values for the variables of interest. Survival curves are presented with time measured in months. It is important to notice that patient survival will be evaluated every six month through medical record, therefore the Interval-censored survival analysis will be applied which simply extends the approach used for right-censored observations to left- and interval-censored observations (Sun 2006). The probability of a left-censored time is the probability that the true time is less than or equal to the censoring time. And, the probability of an interval-censored observation is the probability that the true time is less than or equal to the upper bound of the interval minus the probability that the true time is less than or equal to the lower bound of the interval. The SAS procedure NPMLE could be used. In addition, we will estimate the optimal cut point of [F] FMISO level using

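### Hypoxic volume in mL is tested as an outcome predictor without a tumour-volume term, so an association may partly reflect tumour size and cannot alone support the independent-predictor aim (1.2.a)

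*Combined protocol and SAP*

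**What the plan says.** - **Definition of HV (7.1).** The quantity counted is "The number of pixels in the tumor volume with a T/B ratio" of at least 1.2, converted to millilitres. It is not divided by tumour volume. Section 7.1 and the study procedures in section 5 apply it to the primary tumour and metastases.
- **Use of HV (7.3).** HV at baseline, at each follow-up scan and as a change enters Cox and logistic models one PET variable at a time. Median-split log-rank tests and an ROC cut-point search follow.
- **Adjustment (7.3).** "The set of prognostic variables considered in the analysis include standard clinical measures (age, tumor-node-metastasis status), as well as the PET measurements". A separate sentence also promises adjustment for demographics and further prognostic factors, without listing the latter.
- **Aim 1.2.a.** FMISO uptake before TACE is to be tested as an independent predictor of outcome.
- **Size range (3.1.1).** A mass of at least 3 cm, with no upper limit.
- **Background on size.** Section 2.1.a says hypoxic volume can increase as a solid tumour grows. Section 2.2.d says that earlier studies found no correlation between hypoxic tissue and tumour volume.
- **Published spread of HV (7.2, head and neck cancer).** "the mean HV was 40.2 mL (range 0–1092" mL).

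**The concern.** A large tumour can have a large HV because it is hypoxic or simply because it is large. If size affects survival or response, HV will be associated with outcome even when hypoxia plays no part. Age does not address this, and TNM status can do so only coarsely. The log-rank and ROC analyses have no stated adjustment at all.

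At stake is how an exploratory signal is read. Section 7.3 says these analyses are meant to generate hypotheses for later studies. An HV cut-point or survival split that mostly sorts patients by tumour size would be a poor hypothesis to pass on as evidence about hypoxia.

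**Working it through.** **1. The plan's own figure.** Section 7.2 gives no event count or power for the outcome models. Its precision figure is for the proportion with uptake: "20 patients will be enrolled in this study", "We expect at least 60% hypoxia/uptake", and the design "produces a two-sided 95% confidence interval with a width equal to 0.448 for each FMISO PET scan". With 12 of 20 and the planned "exact 95% confidence interval using the method of Clopper-Pearson", the limits are 0.361 and 0.809, a width of 0.448. This reproduces. The figure matters here only because it fixes N = 20 and suggests that up to about 40% of patients might have little or no HV.

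**2. The bound.** For a sphere, V = (π/6)d³.

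| Diameter | Largest possible HV |
|---|---|
| 3 cm | 14.1 mL |
| 5 cm | 65.4 mL |
| 10 cm | 523.6 mL |

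From 3 to 10 cm the bound rises 523.6/14.1 = 37-fold. A single spherical mass would need a diameter of (6 × 1092/π)^(1/3) = 12.8 cm to contain the largest HV cited in 7.2.

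**3. Expected deaths.** Section 2.1.b cites two-year survival of up to 63% after TACE: 20 × (1 − 0.63) = 7.4. The simulations below average about 8.

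**4. Correlation of HV with volume.** Assumptions, not in the documents: diameters log-uniform from 3 to 10 cm, and a hypoxic fraction distributed Beta(2,3), independent of size and never zero.

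- SD of log V = 3 × ln(10/3)/√12 = 1.043.
- Variance of log fraction = 1/4 + 1/9 + 1/16 = 0.424.
- r = 1.043/√(1.043² + 0.424) = 0.85.
- For 3-6 cm: SD of log V = 0.600, so r = 0.600/√(0.600² + 0.424) = 0.68.

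**5. Spurious HR.** Suppose hazard depends only on volume. To a good approximation, HR per SD of log HV = (HR per SD of log V)^r.

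- HR 1.5: 1.5^0.85 = 1.41 (simulated median 1.40).
- HR 2.0: 2^0.85 = 1.80 (simulated 1.83).
- HR 2.5: 2.5^0.85 = 2.18 (simulated 2.20).
- HR 2.0 with 3-6 cm: 2^0.68 = 1.60 (simulated 1.60).

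**6. Effect of adjustment at N = 20.** Same assumptions, every tumour partly hypoxic. The coarse category is above versus up to 5 cm, a stand-in for TNM.

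| Analysis | HV falsely significant at 5%, for HR 1.5 / 2.0 / 2.5 |
|---|---|
| Cox, HV alone | 11% / 31% / 49% |
| Median-split log-rank | 11% / 26% / 41% |
| Cox with coarse size category | 6% / 11% / 13% |
| Cox with log volume | 5% / 5% / 6% |
| Hypoxic fraction instead of HV | 5% / 4% / 5% |

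**7. Allowing HV of zero.** With 0-40% of patients at zero and HR fixed at 2, the spurious HR per SD of HV is:

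- unadjusted: 1.24-1.80;
- with the coarse category: 1.06-1.46;
- with log volume: 0.96-1.04.

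At 40% zeros, using log(HV + 1), the HV-volume correlation falls to 0.31-0.34. At N = 20 the false-positive rate is then about 10% unadjusted, 6% with the category and 5% with volume.

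**The case against.** - **No prognostic effect of size is documented for this cohort.** This stands. A reader might take section 2.1.b as showing that large tumours do worse. It reports that the advantage of TACE plus SBRT over TACE alone was greater above 3 cm, which is a treatment-by-size interaction. Everyone here has a mass of at least 3 cm and is scheduled for the combination. The HR of 2 is an assumption.
- **The models are not unadjusted.** This stands in part. TNM may carry some size information, and the unlisted prognostic factors leave room for volume. The coarse category removes much of the bias in the working, but not all. An unlisted factor commits the analyst to nothing, and neither point reaches the log-rank and ROC analyses as described.
- **Section 2.2.d denies a correlation with volume.** That would help if hypoxic fraction fell as tumours grew. But no listed study is identified as HCC, the objectives say quantitative hypoxia measurement in HCC has not been done, and section 7 plans no check.
- **The aim is exploratory, with about 7-8 deaths.** True. It limits the importance of the point and the number of covariates any model can carry. T/Bmax, which is not a volume, is analysed separately.
- **Volume could simply replace TNM.** The documents do not support this. HV also covers metastases, so dropping TNM would remove nodal and metastatic status as a control.

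**Conclusion.** The point holds in a limited form. As planned, an association between HV and survival or response may partly reflect tumour size, so it cannot by itself establish HV as an independent predictor under aim 1.2.a.

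The bound on HV and the absence of a volume term follow from the text. The magnitude does not. The spurious HR of about 1.2-1.8 unadjusted, or 1.06-1.5 with a coarse size category, assumes an HR of 2 per SD of log volume, diameters of 3-10 cm, a hypoxic fraction unrelated to size and no effect of hypoxia. It shrinks with a narrower size range or more zero HVs, and vanishes if size has no bearing on outcome.

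A reader might infer that any HV effect would be nothing but tumour size, or that the larger trial would rest on an artefact. Neither is supported. The upper-end HRs are for HV alone with no zeros, whereas the plan adjusts for TNM. Section 7.2 links a larger trial to promising results in general, not to the HV survival model. The primary pre-post analyses and the T/Bmax models are unaffected.

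**What to change.** In 7.3, keep the planned models, including TNM, and add:

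1. Baseline tumour volume, taken from the contour in which HV pixels are counted on the baseline scan.
2. The correlation between baseline HV and baseline tumour volume, reported with the results.
3. For baseline HV, a pre-specified companion Cox and logistic model containing HV and log baseline tumour volume.
4. The log-rank and ROC analyses repeated with hypoxic fraction (HV divided by tumour volume).
5. For follow-up and change-in-HV models, adjustment for baseline volume. Post-treatment volume is itself affected by treatment and overlaps with size-based response, so adjusting for it could remove real signal.
6. A reporting rule: HV is described as an independent predictor only if the association persists in the volume-adjusted or fraction analysis.

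The cost is SAP wording and a few extra outputs. The volume should be available already, because HV pixels are counted within a delineated tumour. The downside is a wider confidence interval for HV, since HV and volume are correlated and only about 7-8 deaths are expected. The result stays exploratory.

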#### **5.4 Duration of Follow Up.**

Being an imaging only trial, we will not be seeing the patients in nuclear medicine after the last imaging is completed. We will be able to obtain clinical follow-up information from medical records generated at clinic visits and update our data base at 6 month intervals, for two years. Final analysis will take place at the completion of patient accrual.

**5.5. Data Collection.** Treatment selection is based on current clinical practices.

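### Section 7.3 takes the six-monthly chart review as the censoring interval for survival, does not separate death from progression, and does not say which survival method governs

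*Combined protocol and SAP*

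**What the plan says.** The survival rule is in section 7.3, in the paragraph on exploratory endpoints: "patient survival will be evaluated every six month through medical record, therefore the Interval-censored survival analysis will be applied". The six months come from section 5.4, where the team will obtain clinical information "from medical records generated at clinic visits and update our data base at 6 month intervals, for two years". The imaging team does not itself see patients after the last scan.

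The same paragraph of 7.3 plans three other methods. Overall and progression-free survival are to be related to the FMISO parameters "using cox regression analysis to correlate" them. "Log-rank tests will be used to compare Kaplan-Meier survival curves associated with patients above and below the median values" of the variables of interest. "Survival curves are presented with time measured in months". The survival time itself is given as follows: "Survival is defined from the time of initial PET scan to the last follow up". Neither section names a date of death or a date last known alive as a data item.

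The second time-to-event endpoint is disease-free survival in section 7.1 and progression-free survival in section 7.3.

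**The concern.** The word *therefore* in the 7.3 sentence carries an inference that does not follow. Interval censoring describes how an event is observed: it is known only to lie between two times at which the patient's state was checked. A six-monthly database update describes when somebody opens the chart. If the chart holds a date of death, that death is observed exactly, and patients still alive are right-censored at the date last known alive. Progression is different. It is found at an assessment and truly lies between two assessments, but those dates are the limits, not the database updates.

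Three things are at stake.

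- An analyst who follows the sentence literally would use limits that are needlessly coarse for dated deaths and wrong for progression.
- Two analysts could follow the same paragraph, one by Cox and one by an interval-censored model, and report different hazard ratios, both in line with the plan.
- If abstractors record only vital status at each update, because the plan asks for no dates, the exact times may never be captured.

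**Working it through.** The plan states no event count, power or precision for survival, so there is no figure of its own to reproduce here. The check has two parts.

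**Logic, by endpoint**

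| Endpoint | How it is observed | Limits implied by 7.3 | Limits that fit |
|---|---|---|---|
| Death, date recorded | exactly | two database updates | none; exact event time |
| Death, date not found | between two contacts | two database updates | last known alive, first known dead |
| Alive at end | right-censored | last follow-up | date last known alive |
| Progression | between two assessments | two database updates | last progression-free and first progressed assessment |

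The 7.3 limits match the observation process in none of the four rows, except by coincidence of dates.

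**Size of the effect**

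Inputs: n = 20 (section 7.2); updates every 6 months for 24 months, so 4 intervals (section 5.4); two-year survival S = 0.63. The last figure is an upper literature figure for TACE in section 2.1.b, not a design assumption, so a range down to 0.20 is shown. Survival is assumed exponential.

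1. Monthly hazard: λ = −ln(0.63)/24 = 0.0193. Expected deaths: 20 × (1 − 0.63) = 7.4.
2. Information on the overall log hazard, grouped relative to exact: with u = 6λ, the ratio is u²e^(−u)/(1 − e^(−u))². At S = 0.63, u = 0.1155 and the ratio is 0.9989.

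| Two-year survival | Expected deaths | Grouped/exact information |
|---|---|---|
| 63% | 7.4 | 0.9989 |
| 50% | 10.0 | 0.9975 |
| 37% | 12.6 | 0.9949 |
| 20% | 16.0 | 0.9866 |

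The loss on the overall hazard is therefore about 0.1% to 1.3%.

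3. The plan's target is a hazard ratio, so the second check is a simulation: n = 20, S = 0.63, one standard-normal marker, Cox on exact times against a grouped proportional hazards model in four 6-month intervals.

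| True HR per SD | Variance of log HR, grouped/exact | Median SE, exact and grouped |
|---|---|---|
| 1 | 1.07 | 0.400 and 0.400 |
| 2 | 1.19 | 0.429 and 0.432 |

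Repeated runs of this scenario gave 1.07 to 1.13 at HR 1 and 1.18 to 1.22 at HR 2. At HR 2 the mean log HR was 0.78 exact and 0.83 grouped, against a true ln 2 = 0.69. Both overshoot, the grouped estimate more.

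4. For two equal groups with an assumed HR of 2, the SD of the log HR was 0.737 exact and 0.756 grouped, so the variance ratio is (0.756/0.737)² = 1.05. With n = 400 in place of 20, the exact/grouped variance ratio was 0.994, so nearly all of the difference disappears. This points to small-sample inflation of the grouped estimate rather than lost information.
5. For scale: detecting HR 2 between two equal groups with 80% power at two-sided 5% needs 4 × (1.960 + 0.842)²/(ln 2)², or 66 deaths. With 7.4 deaths the detectable HR is exp(2.802/√(7.4 × 0.25)) = 7.8.

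**The case against.** The strongest reply is that the documents nowhere say that every death is dated. The source is clinic-visit records, and a death elsewhere may be known only to fall between two contacts. For such a death an interval is right. This stands, and it is why the fix keeps an interval for a death whose date cannot be found.

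A reader might infer that the plan orders known dates to be discarded. It does not. Section 7.3 describes the method as an extension of the right-censored approach, keeps Cox, Kaplan-Meier and log-rank, and is silent on what happens when a date is known. That is a faulty rationale and an unresolved choice of method, not an instruction to coarsen.

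A reader might also infer that confidence intervals would widen, or that a median would be fixed only to within six months. Neither is supported. Median standard errors are almost identical in the simulation. At 63% two-year survival the overall median would be ln 2/0.0193, about 36 months, beyond the 24 months of follow-up.

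Nor are the methods strictly incompatible. Hazard ratios and group tests exist for interval-censored data, and the protocol's reference list includes a generalized log-rank test for them. Months on the time axis are a unit, not a claim of monthly resolution. What remains is that the plan does not say which method applies to which endpoint.

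**Conclusion.** The concern holds as a minor point. The stated reason for interval censoring does not support it for dated deaths, gives the wrong limits for progression, and leaves the governing method for both endpoints open. The survival time also lacks an event and censoring rule, and the second endpoint has two names. Disease-free survival is the less suitable one: patients enter with a tumour of at least 3 cm (section 3.1.1), and section 2.1.b says that TACE rarely eliminates the tumour completely.

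The numerical consequence is modest: roughly 7% (HR 1) to 20% (HR 2 per SD) more variance in the log HR estimate, largely small-sample inflation, with reported standard errors nearly unchanged. These figures rest on exponential survival, 63% alive at two years, a single continuous marker, and the literal reading under which every event time is grouped into six-month intervals. The number of deaths limits these analyses far more than the precision of their dates. The endpoints are exploratory and the primary FMISO analysis is unaffected.

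**What to change.** In sections 5.4 and 5.5, require that each six-monthly review abstract the date of death and the date last known alive, together with the dates of the assessments that bear on progression.

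In section 7.3:

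- Analyse overall survival as right-censored, by Cox, Kaplan-Meier and log-rank. Use an interval only for a death whose date cannot be found.
- Keep interval-censored methods for progression, bounded by the last progression-free and the first progressed assessment dates.
- Replace the present definition of survival with an explicit rule: time from the initial PET scan to death, censored at the date last known alive, and a matching rule for progression or death.
- State which method governs each endpoint.

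Use progression-free survival in both 7.1 and 7.3.

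The cost is a few sentences of plan text and one or two extra date fields from charts that are already being opened. No extra visit, scan or patient is needed.

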ROC analysis based on the optimizations of sensitivity and specificity if there is an association between [F]FMISO level and outcomes. Due to small sample size, this analysis is exploratory in order to identify hypotheses for rigorous evaluation in future studies.

Safety analysis will be descriptive include frequency and proportion of patients have reported AE/SAE, by severity and attribution to study although we don't expect any AE/SAE occurs using the imaging agent based on previous published works.

All analysis will be carried out using statistical analysis software (SAS) v9.4.

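### The FMISO cut point is chosen on outcome in the trial's own 20 patients, after an association screen and with no interval or optimism correction, so any accuracy quoted with it would be too favourable

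*Combined protocol and SAP*

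**What the plan says.** The end of section 7.3 adds a cut-point step to the exploratory analyses. The optimal FMISO level is to be found by "ROC analysis based on the optimizations of sensitivity and specificity if there is an association between" FMISO level and outcomes. What counts as an association is not defined.

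The data are the trial's own patients. Section 7.2 states: "We propose a sample size of 20 patients for this initial clinical trial". No second sample, resampling or optimism correction is mentioned, and no interval is attached to the cut point or its accuracy. Elsewhere section 7.3 does attach intervals: the uptake proportion gets an "exact 95% confidence interval using the method of Clopper-Pearson", and the PET parameters, hazard ratios and odds ratios also get 95% intervals.

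Section 7.3 calls the analysis exploratory because the sample is small, and leaves proper testing to later studies. The T/B threshold of 1.2 in section 7.1 defines hypoxic volume. It is not an outcome cut point.

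**The concern.** Two selections push the same way. The cut point is the one at which these 20 patients separate best, so the separation seen there overstates what new patients would show. The search also runs only for parameters that have already shown an association, so chance associations are over-represented among those that reach it.

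Sections 1 and 7.2 say that the results are meant to inform a larger trial. If a cut point and its apparent accuracy were used for that purpose, a weak or worthless parameter could look much like a good one.

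**Working it through.** **1. Inputs.** From the documents: 20 patients (section 7.2), and a cut point that optimises sensitivity and specificity only if an association is seen (section 7.3). Not in the documents, so assumed: 7 patients with the event and 13 without (range 5 to 10 events); the Youden index as criterion; Mann-Whitney p<0.05 as the screen; a normally distributed marker with equal variance in both groups; and a range of true AUC.

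**2. The plan's own figure.** The documents give no figure for the ROC step. Section 7.2 does give the precision that 20 patients allow for a proportion: "We expect at least 60% hypoxia/uptake" and a "two-sided 95% confidence interval with a width equal to 0.448 for each FMISO PET scan". For 12 of 20 (60%), the Clopper-Pearson limits are 0.3605 and 0.8088, and 0.8088 − 0.3605 = 0.4483, which agrees. Sensitivity rests on the event patients only, so it is less precise still: 8 of 10 has an exact 95% interval of 0.44 to 0.97, before any allowance for the search.

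**3. Formulas.** J(c) = sensitivity(c) + specificity(c) − 1. Apparent J is the largest observed J over all cut points c. True J is the value at that same c in the population: with the marker N(δ,1) in event patients and N(0,1) in the rest, δ = √2·Φ⁻¹(AUC), sensitivity = 1 − Φ(c − δ) and specificity = Φ(c). For AUC 0.7, δ = 1.414 × 0.524 = 0.742, and the best attainable J is 2Φ(0.371) − 1 = 0.289.

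**4. Worthless marker (AUC 0.5, true J = 0), by simulation.**

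| Events of 20 | Mean apparent J, no screen, direction from data | No screen, direction fixed | After p<0.05 screen, direction from data |
|---|---|---|---|
| 5 | 0.40 | 0.27 | 0.69 |
| 7 | 0.37 | 0.25 | 0.63 |
| 10 | 0.34 | 0.23 | 0.61 |

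With 7 events, 369 of 8000 worthless markers passed the screen: 369/8000 = 4.6%. For those, J = 0.63 means sensitivity + specificity = 1.63 where the truth is 1.00.

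**5. Marker with some value.** With 7 events, AUC 0.7 and the screen, apparent J is about 0.67 against a true 0.27. The next table varies the AUC with a 10/10 split and a t-test screen at p<0.05. It shows the mean of sensitivity and specificity, (J + 1)/2.

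| True AUC | Apparent | True | Excess |
|---|---|---|---|
| 0.5 | 0.80 | 0.50 | 0.30 |
| 0.6 | 0.80 | 0.56 | 0.24 |
| 0.7 | 0.81 | 0.63 | 0.18 |
| 0.8 | 0.83 | 0.71 | 0.12 |
| 0.9 | 0.88 | 0.80 | 0.08 |

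From AUC 0.5 to 0.8 the apparent figure hardly moves. With 100 patients per group and AUC 0.7 it is 0.668 against 0.637, an excess of only 0.03.

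**6. Does bootstrap correction repair it?** Without the screen (7 events), apparent, corrected and true J are 0.38, 0.16 and 0.00 at AUC 0.5; 0.48, 0.30 and 0.23 at AUC 0.7; and 0.60, 0.46 and 0.40 at AUC 0.8. More than half of the excess goes, but not all. For a worthless marker that has passed the screen, the corrected value is still about 0.44 to 0.50, with the lower end reached only by repeating the screen in the resamples.

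**The case against.** The strongest reply is that the plan already limits what it claims. The step is labelled exploratory, testing is deferred to new data, section 7.1 says the imaging does not affect treatment, and the primary endpoint is untouched. All of that stands and keeps the point minor. But the label limits the claim without correcting the estimate.

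Four stronger readings are tempting and are not supported.

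- A reader might infer that the plan commits to reporting the optimised sensitivity and specificity, or to carrying the cut point into the next trial. Section 7.3 says only that a cut point will be estimated. Sections 1 and 7.2 speak of the results in general and never mention a cut point.
- A reader might infer that a worthless marker will usually look useful. Under the assumed screen, about 95% of worthless markers get no cut point in any one test, so the unscreened 0.37 does not describe the planned procedure. Several tests do raise the chance of a false trigger: for 10 independent tests at 5% it is 1 − 0.95^10 = 0.40. Section 7.3 itself expects HV and T/Bmax to be highly correlated, which would lower this.
- A reader might extend the criticism to the survival comparison, where "Log-rank tests will be used to compare Kaplan-Meier survival curves associated with patients above and below the median values". A median is fixed without looking at outcome, so it does not carry this optimism.
- A reader might take the bootstrap as a cure. Step 6 of the working shows that it is not.

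It is also fair that sections 1 and 2.1.a state an expected direction (hypoxia goes with resistance). Fixing it in advance lowers the unscreened null figure from 0.37 to 0.25.

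**Conclusion.** The concern holds in this form: the cut point is optimised in the same 20 patients, only after an association is seen, with no interval or correction, so any sensitivity and specificity given with it would be optimistic. With 7 events, the Youden index and a p<0.05 screen, the mean apparent index is about 0.63 against 0 for a worthless marker that passes, and about 0.67 against 0.27 at AUC 0.7. The event split, criterion, screening level, marker distribution and AUC are assumptions. The excess is smallest, about 8 points on the mean of sensitivity and specificity in the 10/10 case, when the true AUC is near 0.9. This is a desirable improvement to an exploratory step and does not bear on the primary endpoint.

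**What to change.** In section 7.3:

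- Remove the condition that an association must be seen first. Report AUC with a 95% CI for every FMISO parameter examined, with the direction of each fixed in advance, as the main ROC result.
- If a cut point is still given, report its bootstrap interval and bootstrap optimism-corrected sensitivity and specificity, repeating the cut-point search in each resample.
- State beside those figures that the correction is only partial at n=20, and that no accuracy is claimed for the cut point until it has been validated in new patients.

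Cost: slightly more analysis and less favourable figures. No extra patients, scans or visits are needed, and the primary analysis does not change.
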